1.2 BACKGROUND ON OCRELIZUMAB

For information on ocrelizumab, see Section 1.2 in Study BN42082 or refer to the Ocrelizumab Investigator's Brochure and/or local prescribing information for details on the nonclinical and clinical studies of ocrelizumab.

1.3 STUDY RATIONALE

This CSF substudy will evaluate the effect of a higher dose of ocrelizumab, compared with the approved dose of ocrelizumab, on biomarkers in CSF and blood in patients with RMS or PPMS. A positive correlation between serum ocrelizumab exposure quartiles and the blood B-cell depletion level was observed in the Phase III studies OPERA I, OPERA II, and ORATORIO data (data on file). The analysis of confirmed disability progression (CDP) for 12 or 24 weeks stratified by exposure quartiles in the Phase III studies indicated that both RMS and PPMS patients with higher exposure have a reduced risk of CDP. This substudy will assess CSF biomarkers, as a proxy for the CNS compartment, using measurements of acute inflammation, chronic inflammation, and neurodegeneration, and measure ocrelizumab concentration in CSF. This may allow determination of whether a higher dose of ocrelizumab has greater effect on biomarkers relevant to B-cell activity or MS pathophysiology, and their relationship to efficacy.

In the OBOE biomarker outcomes trial (ML29966), it was reported that NfL and B-cells decrease in CSF in patients following treatment with ocrelizumab (Bar-Or et al. 2019). However, while blood B-cell depletion is near complete, CSF B-cells are not fully depleted in all patients. The purpose of this optional substudy is to assess whether a higher dose of ocrelizumab has greater impact on NfL and/or B-cell depletion in the CSF, and to assess other MS biomarkers that may relate to exposure, efficacy, or mechanism of ocrelizumab. Patients consenting to the optional substudy will follow all main study procedures. In addition, patients will receive two lumbar punctures (LP) to obtain CSF as part of the substudy: pre-ocrelizumab at baseline and at Week 48 of the double-blind treatment (DBT). Patients will be asked to provide an additional optional sample at Week 24, but this is not required to participate in the substudy. Patients who continue treatment with ocrelizumab in the open-label extension (OLE) will be asked for an additional three optional CSF collections at OLE start, and/or after approximately 4 years of follow-up, and/or at treatment discontinuation.

2. OBJECTIVES AND ENDPOINTS

This CSF substudy will evaluate the effect on CSF biomarkers of a higher dose of ocrelizumab (1200 mg [patient's body weight < 75 kg at baseline] or 1800 mg [patient's body weight ≥ 75 kg at baseline]) intravenous (IV) infusion every 24 weeks in comparison to the approved 600 mg dose of ocrelizumab in patients with RMS.

Specific objectives and corresponding endpoints for the study are outlined below.

2.1 SUBSTUDY OBJECTIVES

2.1.1 Primary Objective

The primary objective for this substudy is to compare a higher dose of ocrelizumab versus the approved dose of ocrelizumab on the basis of the following endpoints:

- Change from baseline at Week 48 in the level of NfL in CSF
- Change from baseline at Week 48 in number of CD19+ B-cells in the CSF (cell number/microliter)

2.1.2 Secondary Objective

The secondary objectives for this substudy are to assess the correlation between changes in CSF biomarkers with those in blood and to compare higher dose of ocrelizumab versus the approved dose of ocrelizumab on the basis of the following endpoints:

- Presence and/or number of OCBs and/or IgG Index at each scheduled visit
- Changes from baseline in levels of B-cell subsets (e.g., naive, memory, plasmablast, etc.) in CSF and blood at each scheduled visit
- Changes from baseline in levels of T cells and/or T-cell subsets (e.g., naive, memory, etc.) in CSF and blood at each scheduled visit

2.1.3 Exploratory Objective

The exploratory efficacy objectives for this substudy are as follows:

- To assess potential correlation between change in blood or CSF biomarkers of neurodegeneration or inflammation and change in MRI or efficacy outcome measures, including but not limited to reduction in Gd-positive MRI lesions, 12-week cCDP, and Expanded Disability Status Scale (EDSS) score.
- To assess changes in peripheral blood mononuclear cells (PBMCs): B- and T-cell numbers, other cell types, activation markers, functional attributes, activity, and/or molecular status of cells; cellular products to include but not be limited to RNA and protein, and levels of soluble inflammatory markers at each scheduled visit

2.2 SAFETY OBJECTIVE

Safety for the study drug will be explored in the main study. Refer to the main study protocol for BN42082.

2.3 PHARMACOKINETIC OBJECTIVE

The PK objectives for this substudy are to characterize the ocrelizumab concentration in CSF and to investigate the relationship between changes in biomarkers in CSF/blood and ocrelizumab concentration in CSF.

2.4 IMMUNOGENICITY OBJECTIVE

Immunogenicity will be explored as part of the main study.

2.5 BIOMARKER OBJECTIVE

The exploratory biomarker objective for this substudy is to identify and/or evaluate biomarkers that are predictive of response to ocrelizumab (i.e., predictive biomarkers), are early surrogates of efficacy, are associated with progression to a more severe disease state (i.e., prognostic biomarkers), are associated with acquired resistance to ocrelizumab, are associated with susceptibility to developing AEs or can lead to improved AE monitoring or investigation (i.e., safety biomarkers), can provide evidence of ocrelizumab activity (i.e., PD biomarkers), or can increase the knowledge and understanding of disease biology and drug safety, on the basis of but not limited to the following endpoints:

- Levels of B-cells/B-cell subsets, T cells/T-cell subsets, and other cell types (e.g., natural killer [NK] cells, monocytes, etc.), functional parameters of B/T/other cell types (activation, cell products), and other biomarkers of inflammation or neurodegeneration/injury in CSF as a reflection of activity in the CNS and compared with blood

3. STUDY DESIGN

[figure not shown]
3.1 DESCRIPTION OF THE STUDY

This study is a substudy of BN42082, which is a Phase IIIb, randomized, double-blind, controlled, parallel group, multicenter study to evaluate efficacy, safety, and pharmacokinetics of a higher dose of ocrelizumab (1200 mg [patient's body weight < 75 kg at baseline] or 1800 mg [patient's body weight ≥ 75 kg at baseline]) intravenous (IV) infusion every 24 weeks in patients with RMS in comparison to the approved 600 mg dose of ocrelizumab.

Patients in BN42082 will be offered the option to join this substudy. Patients consenting to the optional substudy will follow all main study procedures. In addition, patients will receive two LPs to obtain CSF as part of the substudy: pre-ocrelizumab at baseline and at Week 48 of the DBT. Patients will be asked to provide an additional optional sample at Week 24, but this is not required to participate in the substudy. Patients who continue treatment with ocrelizumab in the OLE will be asked for an additional three optional CSF collections at OLE start, and/or after approximately 4 years of follow-up, and/or at treatment discontinuation.

[Figure 3](#) presents an overview of the substudy design. A schedule of activities (SoA) is provided in the substudy SoA in [Appendix A](#) and [Appendix B](#).

Figure 3 Study Design

BD = blood draw; cCDP12 = 12-week composite confirmed disability progression; LP = lumbar puncture; MRI = magnetic resonance imaging.

^a The double-blind treatment period will continue until the last patient completes at least 120 weeks (a minimum of 5 study drug doses with 24 weeks follow-up after 5th dose, with each dose 24 weeks apart) and the target number of cCDP12 events is reached

3.2 END OF STUDY AND LENGTH OF STUDY

The end of the substudy is the same as the end of the main study. For more information, see Section 3.2 in Study BN42082.

In addition, the Sponsor may decide to terminate the substudy at any time.

Analysis of the data generated as a part of this substudy will not commence until unblinding of the main study.

3.2.1 Duration of Participation

The duration of participation of this substudy is the same as the main study. Please see Section 3.2.1 in Study BN42082.

3.3 RATIONALE FOR STUDY DESIGN

3.3.1 Rationale for Ocrelizumab Dose and Schedule

Please see the main study protocol for BN42082 for the ocrelizumab dose and schedule.

3.3.2 Rationale for Biomarker Assessments

MS is a heterogeneous disease. Predictive biomarker samples collected prior to dosing will be assessed in an effort to identify those patients who are most likely to respond better to ocrelizumab. Potential biomarkers will be assessed to demonstrate evidence of biologic activity of ocrelizumab in patients, compared between the dosing arms. As these biomarkers may also have prognostic value, their potential association with disease progression will also be explored.

B-cells are a direct PD biomarker for ocrelizumab, and a correlation with exposure levels to ocrelizumab was observed in the ORCHESTRA Phase III trial. B-cell subsets have been shown to be predictive of drug response (or loss of response) in rheumatoid arthritis patients, with the return of memory B-cell subsets preceding loss of efficacy in anti-CD20 treated patients (Leandro et al. 2006; Adlowitz et al. 2015). PBMC are also used to assess the levels of B-cell subsets, T cells (which may also respond to ocrelizumab treatment if they express CD20 [Palinchamy et al. 2014]), and to assess B- and T-cell function *in vitro* assays as potential PD, prognostic, or predictive biomarkers.

Biomarkers of neuroinflammation, such as NfL chain, an acute neuronal injury marker, have been correlated with Gd-enhancing MRI lesions and clinical relapses (Burman et al. 2014) and with response to drug treatment in PMS and RMS (Gunnarsson et al. 2011; Axelsson et al. 2014; Kuhle et al. 2019). NfL can be detected in the blood, and blood levels are correlated with CSF levels (DiSanto et al. 2017). Other key sensitive CSF biomarkers of disease include B-cell products such as the presence of OCBs, or antibodies produced in the CSF (Link and Huang 2006), as well as the presence of intrathecal memory B-cell plasmablasts (Cepok et al. 2005). Cellular dynamics and the cellular protein of RNA products of cells may allow for an understanding of mechanistic effects of ocrelizumab. These biomarkers suggest a link between B-cell activity and MS pathology, and may act as PD, prognostic, or predictive biomarkers.

4. MATERIALS AND METHODS

4.1 PATIENTS

Up to 144 patients with RMS from the main study will be enrolled in this substudy.

4.1.1 Inclusion Criteria

Patients must meet the following criteria for the substudy entry:

- Meet all inclusion criteria to participate in the main study protocol for Study BN42082.
- Signed Informed Consent Form (ICF) for the optional substudy

- Ability to comply with the substudy protocol, including LPs, in the investigator's judgment

4.1.2 Exclusion Criteria

Patients who meet any of the following criteria will be excluded from study entry:

- Patients excluded by any exclusion criteria outlined for in the main study protocols for BN42082
- Systemic corticosteroid therapy within 4 weeks prior to baseline (e.g., for recent relapse or chronic use)
 - The screening period may be extended (but cannot exceed 6 weeks) for patients who have used systemic corticosteroids for their MS before screening.
- Previous use of anti-CD20s is allowed if the last infusion was more than 2 years before screening, B-cell count is normal, and the stop of the treatment was not motivated by safety reasons or lack of efficacy
- Previous treatment with any other immunomodulatory or immunosuppressive medication not already listed in the main study exclusion criteria without appropriate washout as described in the applicable local label

4.2 METHOD OF TREATMENT ASSIGNMENT AND BLINDING

Refer to the main study protocol for Study BN42082.

4.3 STUDY TREATMENT AND OTHER TREATMENTS RELEVANT TO THE STUDY DESIGN.

Refer to the main study protocol for Study BN42082 for all information relating to formulation, packaging, dosage, administration, treatment discontinuation, compliance, handling, accountability and/or continued access to drug.

4.4 CONCOMITANT THERAPY

Refer to the main study protocol for Study BN42082 for all information relating to prohibited or permitted therapies.

4.5 STUDY ASSESSMENTS

The SoA to be performed during the substudy is provided in [Appendix A](#) and [Appendix B](#). All activities should be performed and documented for each patient.

4.5.1 Informed Consent Forms and Screening Log

Written informed consent for participation in the substudy must be obtained before performing any substudy-related procedures (including screening evaluations). ICFs for enrolled patients and for patients who are not subsequently enrolled will be maintained at the study site.

All screening evaluations must be completed and reviewed to confirm that patients meet all eligibility criteria before enrollment. The investigator will maintain a screening log to record details of all patients screened and to confirm eligibility or record reasons for screening failure, as applicable.

The screening data for all patients (including those who have been screen failed) will be captured by the sites in the eCRF.

4.5.2 Medical History, Baseline Conditions, Concomitant Medication, and Demographic Data

Refer to the main study protocol Study for BN42082 for reporting of all demographic, concomitant medication and medical history data.

4.5.3 Laboratory, Biomarker, and Other Biological Samples

For sampling procedures, storage conditions, and shipment instructions, see the laboratory manual.

Unless the patient gives specific consent for their leftover samples to be stored for optional exploratory research (see Section 4.5. in the main protocol), biological samples will be destroyed no later than the time of completion of the final Clinical Study Report, with the following exceptions:

- Serum or CSF samples collected for PK analysis may be needed for additional immunogenicity characterization and for PK assay development and validation; therefore, these samples will be destroyed no later than 15 years after the final Clinical Study Report has been completed.
- Serum, PBMC or CSF samples collected for biomarker research and biomarker assay development will be destroyed no later than 15 years after the final Clinical Study Report has been completed.

When a patient withdraws from the study, samples collected prior to the date of withdrawal may still be analyzed, unless the patient specifically requests that the samples be destroyed, or local laws require destruction of the samples. However, if samples have been tested prior to withdrawal, results from those tests will remain as part of the overall research data.

Data arising from sample analysis, including data on genomic variants, will be subject to the confidentiality standards described in Section 8.4.

Given the complexity and exploratory nature of exploratory biomarker analyses, data derived from these analyses will generally not be provided to study investigators or

patients unless required by law. The aggregate results of any conducted research will be available in accordance with the effective Sponsor policy on study data publication.

4.5.4 Study Procedure Risk Mitigation

The risk of headache post-LP can be mitigated by expert nurse practitioner or physician collection of the sample, and the use of smaller atraumatic needles (e.g., Sprotte). Atraumatic needles will be provided to sites and personnel with expertise in LP will perform collection in order to minimize such risk.

Spinal epidural or subdural hematoma and brain and spinal hemorrhage are rare but potentially serious complications of an LP. The following precautions are therefore advised:

- Exclude coagulation abnormalities or coagulation results outside the normal range or platelet count below $500 \times 10^9/L$
- Exclude coagulopathies and uncorrected bleeding diathesis
- Discontinue anticoagulant treatments to minimize hemorrhagic risks if medically justifiable
- Patients with dual platelet therapy (ASS and clopidogrel) should discontinue clopidogrel 1 week before the puncture if medically justifiable

Please also refer to the local standard practice recommendations in your country/ at your site, especially if more stringent.

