3.1.1.3 Optional Open-Label Extension Phase

Following database lock of the DBT, patients should continue to receive blinded treatment until the primary analysis is completed and the decision to start the OLE is

communicated by the Sponsor. If the result of the primary analysis is positive, an optional higher dose extension treatment (OLE phase) is planned for eligible patients who have adhered to the DBT until the primary analysis and, in the opinion of investigator, could benefit from a higher dose of ocrelizumab. The OLE will be carried out for approximately 96 weeks (4 doses in total) starting from the first OLE dose. The 96-week duration of the OLE phase serves to further evaluate long-term safety and efficacy of a higher dose of ocrelizumab (of note, the currently approved 600 mg dose of ocrelizumab will not be offered in this extension phase).

During the OLE phase, patients originally randomized to the higher dose group will continue with their assigned dose of ocrelizumab (either 1200 or 1800 mg). Patients who were assigned to the control group and received 600 mg ocrelizumab in the DBT, will be offered a higher dose of ocrelizumab, based on their body weight at OLE baseline.

The blinding procedures are not necessary during the OLE phase. All required assessments during the OLE phase should occur as described in OLE schedule of activities (see [Appendix 2](#)).

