Appendix 2: Schedule of Activities: Open-Label Extension

	OLE Screening	OLE								Delayed Dosing Visit ^a	Unschd. Visit ^b	Tx Discon. Visit ^c
Dose ^w		1		2		3		4				
Visit		1	2	3	4	5	6	7	8			
Study week		Wk 0	Wk 22	Wk 24	Wk 46	Wk 48	Wk 70	Wk 72	Wk 96			
(Window in days)	-30 to -1		(±7)	(±5)	(±7)	(±5)	(±7)	(±5)	(±5)			
Administration (infusion) of ocrelizumab (higher dose) ^p		x		x		x		x		x		
Concomitant medications ^q	x	x	x	x	x	x	x	x	x	x	x	x
Adverse events ^r	x	x	x	x	x	x	x	x	x	x	x	x
MRI (every 48 weeks) ^s		(x)		(x)		(x)		(x)	(x)			x
ADA sample (serum) ^t		x				x						x
Biomarker plasma sample ^u		x				x			x		x	x
Biomarker serum sample ^u		x				x			x		x	x
HBV DNA (if required) ^v	x	x	x		x		x		x			x

9-HPT = 9-Hole Peg Test; ADA = anti-drug antibody; AE = adverse event; COVID-19 = coronavirus disease 2019; Discon. = discontinuation; eCRF = electronic Case Report Form; EDSS = Expanded Disability Status Scale; EQ-5D-5L = EuroQol 5-Dimension, 5-Level Questionnaire; FSH = follicle stimulating hormone; HBcAb = hepatitis B core antibody; HBsAg = hepatitis B surface antigen; HBV = hepatitis B virus; MFIS = Modified Fatigue Impact Scale; MRI = magnetic resonance imaging; MS = multiple sclerosis; MSIS-29 = Multiple Sclerosis Impact Scale-29; MSWS-12 = Multiple Sclerosis Walking Scale-12 item; Neuro-QoL UE = Quality of Life in Neurological Disorders Upper Extremity Function; OLE = open-label extension; PCR = polymerase chain reaction; PGI-C = Patient Global Impression of Change; PGI-C-UL = Patient Global Impression of Change of Upper Limb function; PGI-S = Patient Global Impression of Severity; PK = pharmacokinetic; PML = progressive multifocal leukoencephalopathy; PRO = patient reported outcome; SDMT = Symbol Digit Modalities Test; T25FWT = Timed 25-Foot Walk test; Tx = treatment; Unschd. = unscheduled; Wk = week; (x) = every 48 weeks.

Note: All assessments should be performed on the day of the scheduled visit, unless otherwise specified. On infusion days, all assessments should be performed prior to dosing, unless otherwise specified.

- ^a A delayed dosing visit will be performed and recorded in the Delayed Dosing Visit eCRF when dosing cannot be administered at the scheduled dosing visit. Other tests or assessments may be performed as appropriate.
- ^b Assessments at unscheduled (non-dosing) visits may be performed as clinically appropriate.
- ^c Patients who discontinue study drug prematurely will return to the clinic for a treatment discontinuation visit.

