- ^d The collection of the CSF specimen at baseline should ideally not occur within the first 10 days of the brain MRI at screening (and not earlier than 6 days following the brain MRI at screening), to avoid contamination with gadolinium in the biomarker CSF sample. The collection of the CSF specimen should precede the brain MRI at Week 24 and Week 48, to avoid contamination with gadolinium in the biomarker CSF sample. In order to facilitate scheduling before an ocrelizumab dose (e.g., at Week 24 or Week 48), the CSF specimen, followed by the brain MRI, may precede the administration of ocrelizumab by up to 7 business days.
- ^e A fresh whole blood sample to be collected on the same day of CSF collection to be processed locally with CSF for flow cytometry analysis. Blood sample should be collected prior to the methylprednisolone injection if at a dosing visit and will be drawn for baseline and indicated post-dose samples.
- ^f PBMC cells will be collected from two fresh whole blood samples at indicated timepoints in Schedule of Assessments and sent to the central lab for processing. PBMC samples should be collected prior to the methylprednisolone injection if at a dosing visit and will be drawn for baseline and indicated post-dose samples.
- ^g Adverse events resulting from any substudy procedure (e.g., lumbar puncture, blood draw) should be recorded at any visit, as close to the occurrence of the event as possible.
- ^h Patients will be asked to give optional treatment discontinuation CSF and matched blood samples, if no other post-dose samples have been collected.

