Appendix B

Substudy Open-Label Extension Schedule of Activities

	OLE Screening	OLE								Delayed Dosing Visit	Unsched. Visit	Tx Discon. Visit
Dose		1		2		3		4				
Visit		1	3	4	5	6	7	8	9			
Study week		Wk 0	Wk 22	Wk 24	Wk 46	Wk 48	Wk 70	Wk 72	Wk 96			
(Window in days)	-30 to -1	-14	(±7)	(±5)	(±7)	(±5)	(±7)	(±5)	(-14)			
Review of substudy eligibility criteria	x	x										
Main study OLE visits ^a	x	x	x	x	x	x	x	x	x	x	x	x
Informed consent for the substudy OLE	x											
CSF collection for cellular and fluid biomarker analysis ^{b, c}		(x)							(x)			(x)
CSF sample for PK ^{b, c}		(x)							(x)			(x)
Biomarker serum sample ^d		(x)							(x)			(x)
Whole blood collection for flow cytometry ^e		(x)							(x)			(x)
Blood for PBMC ^f		(x)							(x)		x	(x)
Adverse event collection ^g		(x)							(x)			(x)

CSF = cerebrospinal fluid; Discon. = discontinued; IgG = immunoglobulin G; MRI = magnetic resonance imaging; OCB = oligoclonal bands; OLE = open-label extension; PBMC = peripheral blood mononuclear cell; PK = pharmacokinetic; Tx = treatment; Unsched. = unscheduled; Wk = week.

- ^a Patients in the substudy OLE should follow all main study procedures as outlined in the main study SOA [Appendix 2](#)
- ^b Optional CSF collection to be collected at OLE Week 0, and/or Week 96, and/or treatment discontinuation, sample should be collected before administration of ocrelizumab and prior to the methylprednisolone injection if at a dosing visit. CSF samples to be collected on same day of blood collection to facilitate comparison to OCB/IgG Index.
- ^c The collection of the CSF specimen should precede any brain MRI at OLE Week 0, and/or Week 96, and/or treatment discontinuation, to avoid contamination with gadolinium in the biomarker CSF sample. In order to facilitate scheduling before an ocrelizumab dose (e.g., at OLE Week 0), the CSF specimen, followed by the brain MRI, may precede the administration of ocrelizumab by up to 7 business days.
- ^d ONLY collect blood for biomarker serum sample IF the optional CSF sample is collected, blood samples for serum will be collected at OLE Week 0 and/or 96 weeks. Blood should be collected on same day of CSF collection to facilitate OCB/IgG Index measurement. Blood sample should be collected before administration of ocrelizumab and prior to the methylprednisolone injection if at a dosing visit.

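### The CSF substudy's platelet minimum of 500 × 10^9/L before lumbar puncture is wrong as written: about 97.5% or more of patients would be expected to fall below it

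*Protocol*

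**What the plan says.** Protocol Appendix 18, section 4.5.4, names spinal hematoma and brain or spinal hemorrhage as rare but serious complications of LP, and advises four precautions. The first is "Exclude coagulation abnormalities or coagulation results outside the normal range or platelet count below $500", in units of × 10^9/L (the dollar sign is markup from reading the PDF). The others concern bleeding disorders, anticoagulants and dual antiplatelet treatment.

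On post-LP headache, the same section says that "personnel with expertise in LP will perform collection in order to minimize such risk". It closes with "Please also refer to the local standard practice recommendations in your country/ at your site, especially if more stringent".

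On numbers, substudy section 4.1 states: "Up to 144 patients with RMS from the main study will be enrolled in this substudy". LPs are required at baseline and Week 48, with an optional one at Week 24. For the extension, Appendix B of the substudy adds: "Optional CSF collection to be collected at OLE Week 0, and/or Week 96, and/or treatment discontinuation".

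**The concern.** The precaution is there to prevent bleeding, so only a low platelet count matters, and excluding counts under 500 makes 500 a minimum. On any ordinary view of adult platelet counts, that minimum lies at or above the top of the normal range. A site applying it as written would find nearly every patient unsuitable for the procedure that defines the substudy.

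What is at stake is the usability of one decision threshold in the safety section for an invasive procedure done only for research. A limit that nearly everyone fails will probably be set aside, which leaves each site to choose its own cutoff.

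**Working it through.** **1. Is there a figure to reproduce?** No. The 500 limit has no derivation or source in the documents. The check is therefore one of plausibility.

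**2. Does another section supply a usable limit?** No.
- Main exclusion criteria (Protocol 4.1.2): no platelet criterion.
- Substudy criteria (Appendix 18, 4.1.1 and 4.1.2): no platelet criterion.
- Hematology lists (Protocol 4.5.8; notes to Appendices 1 and 2): the platelet count is listed, with no limit or reference range.
- Clarification letter of 22 November 2024: six items, none on this.
- Local-practice sentence in 4.5.4: it stresses stricter local rules. A site guideline with a lower platelet minimum is less strict, so the sentence does not clearly allow a site to relax 500.

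**3. What share of patients falls below 500?** The reference range is my assumption. Take L to U as the central 95% of platelet counts (× 10^9/L).

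Normal: mean m = (L + U)/2, SD s = (U − L)/(2 × 1.96), share below = Φ((500 − m)/s).

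Lognormal: the same formulas with ln L, ln U and ln 500.

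Example, 150–450:
- Normal: m = 300, s = 300/3.92 = 76.5, z = 200/76.5 = 2.61, share = 0.9955.
- Lognormal: m = (ln 150 + ln 450)/2 = 5.560, s = 1.0986/3.92 = 0.280, z = (6.215 − 5.560)/0.280 = 2.34, share = 0.9903.

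| Assumed range | Below 500, normal | Below 500, lognormal | Expected below, of 144 |
|---|---|---|---|
| 150–350 | >99.99% | 99.98% | 144.0 / 144.0 |
| 150–400 | 99.98% | 99.78% | 144.0 / 143.7 |
| 150–450 | 99.55% | 99.03% | 143.4 / 142.6 |
| 140–450 | 99.52% | 98.97% | 143.3 / 142.5 |
| 150–500 | 97.5% | 97.5% | 140.4 / 140.4 |

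The last row is deliberately generous: it makes 500 the upper limit of normal, so 97.5% follows by construction.

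A second parametrization, with mean/SD pairs from 220/50 to 300/80, gives 99.4% to more than 99.99% (normal) and 98.1% to 99.99% (lognormal).

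**4. Which LPs could a correction still affect?** SAP 2.2 places the last randomizations in August 2022. Adding 48 weeks (336 days) to 31 August 2022 gives 2 August 2023 for the last required LP. This assumes no dose delay, and Appendix 1 of the protocol does allow later doses to shift. On that schedule the required LPs were due before protocol version 4 (21 December 2023). What remains is chiefly the optional OLE LPs. There is also a double-blind discontinuation LP, under a narrow condition: "Patients will be asked to give optional treatment discontinuation CSF and matched blood samples, if no other post-dose samples have been collected". The OLE itself is conditional: "If the result of the primary analysis is positive, an optional higher dose extension treatment (OLE phase) is planned for eligible patients".

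**The case against.** **The numeral may be a reading error.** The text comes from a PDF read by a program, and a lost decimal point or misread digit would remove the point. This stands as a reason to check the page first. Nothing in the documents shows such an error.

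**The percentage has no basis in the documents.** It is an assumption, and 97.5% is the lowest value among the ranges tried and not a mathematical floor. The conclusion holds across every range.

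**It is only advice.** This stands. The precautions are advised, the binding criteria contain no platelet rule, and ability to comply with LPs is left to the investigator's judgment. Coagulation tests appear in the same bullet but in none of the protocol's laboratory lists, which suggests that the pre-LP work-up is left to sites.

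**It cannot harm anyone.** Largely right: a minimum set too high errs toward fewer LPs.

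A reader might infer more than the documents support:
- *That LPs were refused or the substudy could not enroll.* No document reports this, and advice does not bar anyone.
- *That patients were exposed to extra bleeding risk.* The error runs the other way, and experienced staff, the other precautions and local practice still apply.
- *That 50 was meant, with one zero too many.* Possible: under the same ranges about 0.1% or fewer would fall below 50. The documents do not confirm it, and the value is a medical decision.
- *That the trial's results are affected.* The clarification letter classes the substudy analyses as exploratory, and the substudy is optional.

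**Conclusion.** Wrong as written; severity minor. As a minimum before LP, 500 × 10^9/L would advise against nearly all substudy LPs if taken literally: about 97.5% or more of patients fall below it, or roughly 140 to 144 of 144. No other section offers a usable limit.

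This rests on two assumptions: that the extracted figure matches the published page, and that platelet counts in these patients resemble one of the ranges tried. The consequence is an unusable advisory threshold in an optional substudy. No main-trial endpoint, analysis or sample size changes.

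**What to change.** 1. Check the figure in Appendix 18, section 4.5.4, against the published protocol page and the sponsor's source for LP safety.
2. If 500 stands, replace it by clarification letter with the intended minimum, set by the sponsor's medical team. Do this before any optional OLE LP (Week 0, Week 96 and/or treatment discontinuation).

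The main cost is one corrected figure, in a type of letter the sponsor already uses. There may be a small practical cost too. OLE hematology includes platelets at screening and at Weeks 0, 22, 46, 70 and 96, but those samples go to a central laboratory, and the substudy window for the Week 96 LP opens 14 days before the visit. For an LP early in that window the latest scheduled count would be Week 70, so the Week 96 draw may need to move forward or a local count may be needed.
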